6.10.2. Analysis of tertiary objective: co-infections with RSV

For cases of WHO RSV LRTI and WHO RSV severe LRTI the number and percentage of cases associated with at least one other respiratory virus, 1, 2, or more than 2 viruses will be described. The number and percentage of cases associated with each of the other respiratory viruses will be described.

This analysis will be performed at less than 3 month, between 3 - 5 month, 6 - 11 month, and 12 - 23 months and by country.

6.11. Evaluation of cord blood collection variables, disease surveillance and protocol procedures

6.11.1. Analysis of tertiary objective: cord blood collection, storage and processing

The objective is to assess the effect of cord blood collection, and storage and processing on the neutralizing antibody level in the cord blood.

Number and percentage of subjects follow each cord-blood collection, storage, and processing categories will be calculated. Descriptive statistics of geometric mean, standard deviation, median, and range will be calculated for neutralizing antibody level in the cord blood for each of the collection, storage, and processing category.

The duration between collection and completion of processing will be calculated. Scatter plots will be used to assess the association between the duration of processing and cord blood antibody levels.

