6.5.5. Collection of cord blood sample

Refer to the Module on Biospecimen Management in the SPM for general handling of blood samples.

A volume of up to approximately 10 mL of whole cord blood sample will be collected from all subjects at birth, which should yield up to approximately 3 mL of serum. In case

less than 3 mL of whole blood is collected, the subject will be considered a screening failure and the sample collected needs to be discarded according to local procedure.

Details of the sample collection such as duration of processing steps and storage conditions need to be collected and recorded in the eCRF in order to allow adjustment for these variables in the primary analyses and to explore the impact of collection variables on the measured antibody titer.

Cord blood samples collected will provide RSV- antibody levels in the child, at birth.

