The measured maternal antibody levels by storage condition or tube type will be analysed graphically and by group statistics (mean, 95% CI). Group means will be compared by t-test to assess the statistical significance of differences.

The measured maternal antibody levels in samples collected 'according to recommended procedure' and 'not according to recommended procedure' will be analysed graphically and by group statistics (mean, 95% CI). Group means will be compared by t-test to assess the statistical significance of any difference.

• To assess the impact of potential RSV risk factors (e.g. complications at birth, family history of respiratory disease, lifestyle characteristics and household composition, breast feeding, passive smoking, day care attendance) on the incidence and severity of RSV-associated LRTI.

The incidence of any, severe, non-severe RSV-associated LRTI will be analysed using a Poisson regression model including potential risk factors.

• To assess the natural decay of maternal antibody levels using a single follow-up blood sample collected from a randomly selected sub-cohort of subjects at 2, 4, 6, 12, 18 and 24 months.

The primary analysis will be based on ATP sub-cohort for this objective.

The decay of maternal antibody levels over time will be analysed graphically and by a log-linear regression. A true, natural decay curve will be explored by stochastically reducing the sample to uninfected subjects only. The following steps will be taken to identify, confirmed and suspected infected subjects to eliminate these from the sample;

- Subjects with an RSV positive nasal swab during the study before time of sampling will be eliminated.
- A sensitivity analysis of the decay curve will be explored in sub-sample consisting of the subjects born 'off-season' as these have the lowest likelihood of having been infected.
- Subjects with an antibody titer at the sampling time that is more than 2-fold above the expected value based on their baseline (cord blood) value and the established decay curve will be considered to have been infected, eliminated and the decay curve refined.
- Step 3 is repeated up to 5 times until the most accurate decay curve is established.

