12.8. Practical implementation of protocol

12.8.1. Cord blood collection, storage, and processing

Template 56 Number and percentage of subjects according to the storage process of the cord blood sample, Overall and by country (PPS)

			Tot N=	al
Country	Characteristics	Categories	n	%
Overall	Cord storage condition until blood collection	Refrigerated		
		Wet ice		
		Room temperature		
		Processed immediately		
	Type of tube used to collect cord blood	Quest tube		
		Plain tube		
		Tube with gel separator		
		Other		
	Storage of the cord blood sample	Refrigerated		
		Wet ice		
		Room temperature		
		Processed immediately		
	Storage of the serum sample	Refrigerated		
		Wet ice		
		Room temperature		
		Processed immediately		
<each country=""></each>				

N = total number of subjects

n/% = number / percentage of subjects in a given category

Template 57 Duration between collections and completion of processing of cord blood sample (PPS)

		То	tal				
Country	Process duration	n	Mean	SD	Median	Minimum	Maximum
Overall	Duration of overall process (hours)						
	Duration of process between collection and centrifugation (hours)						
	Duration of process between centrifugation and transfer of serum (hours)						
	Duration of process between transfer of serum and storage (hours)						
Each country							

Overall process duration: Duration of process between collection and storage of cord blood sample

n= Number of subjects with cord blood sample in each country considered SD=Standard Deviation

200150 (EPI-RSV-005 BOD)

Statistical Analysis Plan Amendment 1 Final

Template 58 Descriptive statistics of [RSV-A - RSV-B] maternal antibody levels in cord blood according to [Storage condition until blood collection -Storage condition until centrifugation - Storage condition until tube was frozen] (PPS)

	[RSV N=	'-A –RSV	'-B] mater	nal a	ntib	odies		
Storage condition until blood collection	n	GMT	95% CI	SD	Q1	Median	Q3	Min/Max
Refrigerated								
Wet ice								
Room temperature								
Processed immediately								

N = total number of subjects

n= Number of events in each category

GM = Geometric mean SD=Standard Deviation

 $Q1 \text{ and } Q3 = 1^{st} \text{ and } 3^{rd} \text{ quantiles}$

Min/Max = Minimum/Maximum

Template 59 Descriptive statistics of [RSV-A - RSV-B] maternal antibody levels in cord blood according to tube type (PPS)

	[RSV N=	-A –RSV	'-B] mater	nal a	ntib	odies		
Storage condition until blood collection	n	GMT	95% CI	SD	Q1	Median	Q3	Min/Max

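### Cord-blood titres by storage condition and tube type are pooled over eight countries without adjustment, so a handling effect cannot be separated from country differences where handling varies by country

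*SAP*

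**What the plan says.** The aim in SAP 6.11.1 is worded as an effect: "The objective is to assess the effect of cord blood collection, and storage and processing on the neutralizing antibody level in the cord blood". For categorical handling variables the method is: "Descriptive statistics of geometric mean, standard deviation, median, and range will be calculated for neutralizing antibody level in the cord blood", by category. For processing time it is: "Scatter plots will be used to assess the association between the duration of processing and cord blood antibody levels". No country stratum or model term is named.

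The shells in SAP 12.8.1 follow that text. Template 58 tabulates "maternal antibody levels in cord blood according to [Storage condition until blood collection" and two later storage steps; its rows are four storage conditions. Template 59 tabulates "maternal antibody levels in cord blood according to tube type (PPS"); its rows are four tube types. Both show the GMT with 95% CI, and neither has a country row or column. Template 60 plots log10 titre against processing durations, but its figure is not in the text available.

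Country is used nearby. Template 56 gives "Number and percentage of subjects according to the storage process of the cord blood sample, Overall and by country (PPS"), without titres. Template 57 gives durations by country, also without titres. Template 40 gives cord-blood GMT by country, without handling.

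Protocol 9.7.3 describes the same objective with log-linear regression on duration and, for storage condition and tube type, this comparison: "Group means will be compared by t-test to assess the statistical significance of differences". It names no country adjustment either. SAP section 9 moves the cord-blood analysis to descriptive statistics, and SAP section 7 rules out hypothesis testing.

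**The concern.** The question is whether handling changes the measured titre. That needs samples handled differently but otherwise alike. A table pooled over eight countries compares children from places that used one method with children from places that used another. If those places also differ in maternal RSV antibody, the difference between rows mixes the two.

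Country is a plausible confounder on the plan's own terms. Protocol 6.7.1 lets sites use their own collection and storage materials where the sponsor supplies none. The SAP reports handling by country and titre by country, and lists country of birth as a candidate covariate in the cord-antibody models (6.9.1). In section 9 it also limits incidence subgroups to country because pooling such varied settings is uninformative, but it does not carry that reasoning to 6.11.1.

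At stake is the reading of Templates 58 and 59. A population difference could be taken for sample instability, or a real loss of titre could be masked.

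**Working it through.** The documents give no sample size, effect size or error rate for this objective, so there is no planned figure to reproduce.

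**Step 1: what each planned output combines.**

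| Output | Titre | Handling | Country |
|---|---|---|---|
| Template 40 | yes | no | yes |
| Template 56 (storage, tube) | no | yes | yes |
| Template 57 (durations) | no | yes | yes |
| Templates 58, 59 | yes | yes | no |
| Template 60 | yes | yes | none in title; plot not shown |

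For storage condition and tube type, no table or model brings all three together.

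**Step 2: size of the bias when handling has no effect.** All inputs here are assumptions. Take two country groups of equal size, with a GMT ratio R between the high-titre and low-titre group. A share a of the high group and a share b of the low group use condition A.

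- Share of A samples from the high group: hA = a/(a+b)
- Share of B samples from the high group: hB = (1−a)/((1−a)+(1−b))
- Pooled GMT ratio, A to B: R^(hA−hB)

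Example: a = 0.75, b = 0.25 gives hA = 0.75 and hB = 0.25, so hA−hB = 0.50. With R = 1.5 the pooled ratio is 1.5^0.50 = 1.22, although the true ratio is 1.00.

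| Use of A, high/low group | hA−hB | R = 1.25 | R = 1.5 | R = 2.0 |
|---|---|---|---|---|
| 50% / 50% | 0 | 1.00 | 1.00 | 1.00 |
| 60% / 40% | 0.20 | 1.05 | 1.08 | 1.15 |
| 75% / 25% | 0.50 | 1.12 | 1.22 | 1.41 |
| 90% / 10% | 0.80 | 1.20 | 1.38 | 1.74 |
| 100% / 0% | 1.00 | 1.25 | 1.50 | 2.00 |

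With R = 1 every entry is 1.00. The country-stratified ratio is 1.00 in the first four rows. In the last row it cannot be estimated, because no country group uses both conditions.

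**Step 3: size of the bias when handling has a real effect.** Suppose condition A truly loses 20% of titre (ratio 0.80), with R = 1.5 and 75/25 use.

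- A used mostly in high-titre countries: 0.80 × 1.22 = 0.98, so the loss is hidden.
- A used mostly in low-titre countries: 0.80 / 1.22 = 0.65, so the loss is exaggerated.

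The within-country ratio is 0.80 in both cases.

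**The case against.** The strongest reply is that this is a tertiary, exploratory objective with descriptive output, and that Templates 40, 56 and 57 already let a reader see whether handling and titre vary by country. That stands as a limit on importance. It does not answer the point, because those tables show the imbalance without correcting for it, and calling a comparison descriptive does not remove confounding.

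Second, nothing shows that handling does vary by country. Protocol 6.5.5 refers all sites to a common procedures manual, and 6.7.1 makes sponsor materials mandatory where supplied. That also stands, which is why the conclusion is conditional.

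Three stronger readings are tempting, and the documents do not support them.

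- A reader might infer that the plan will test pooled groups and often reject falsely. SAP 6.11.1 lists no test and section 7 excludes testing, so the t-test in Protocol 9.7.3 is not part of the current analysis. False-rejection rates would describe an analysis nobody plans to run.
- A reader might infer that a wrong answer here passes into the cord-antibody models. Protocol 6.5.5 says handling details are recorded "in order to allow adjustment for these variables in the primary analyses and to explore the impact of collection" variables on titre. Those are parallel purposes; neither is made to depend on the other. The Cox covariates in SAP 6.9.1 and Table 15 include no handling variable, so no such route is planned.
- A reader might infer that Template 60 is certainly pooled. Its plot is not shown, and a title that omits country proves little: Template 57's title omits it too, yet its shell has country rows.

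**Conclusion.** The point holds in a limited form. As specified, SAP 6.11.1 with Templates 58 and 59 cannot separate a handling effect from country differences in maternal titre, to the extent that both vary by country. The bias lies between nil and the full country ratio. Where it falls depends on the handling mix and the country titres, neither of which the documents give; the figures above only illustrate the range.

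It would be too strong to say that the tables show country differences instead of sample stability. That requires complete separation of methods by country; short of it, the estimate mixes the two. This is a minor weakness in a tertiary, descriptive analysis, worth correcting because the correction is cheap.

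**What to change.** In SAP 6.11.1 and section 12.8.1:

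- Add country rows to Templates 58 and 59.
- Mark points by country in Template 60, or panel it by country.
- Report country-adjusted GMT ratios with 95% CI from a linear model of log10 titre on the handling variable plus country, using the substitution below the assay cut-off already set in SAP 6.1.3.
- Flag any category that occurs in only one country, and any country with only one category, since neither gives a within-country contrast.

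The cost is a text edit, extra table rows and simple regressions on data the plan already collects. The downside is wider intervals, or contrasts that cannot be estimated, where a country uses a single method. That is an accurate statement of what the data can show there.

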6.11.2. Analysis of tertiary objective: evaluation of surveillance and protocol procedures

The objective of these sets of analysis is to evaluate the practical implementation of the surveillance system across the countries.

The number and percent of surveillance contacts resulted in an exam visit will be summarized by country. The number and percent of exam visit following under each duration period after surveillance contact is summarized by country. The number of exam visit associate with a surveillance contact is summarized by country. The number and percent of visit with collection of nasal swab is summarized by country. And the number and percent of nasal swab under each duration period after onset of coughing or difficult breathing is summarize by country.

7. ANALYSIS INTERPRETATION

Analyses will be descriptive with the aim to characterise overall occurrences, patterns and potential differences between groups in the endpoints related to the objectives. No hypothesis testing will be performed.

The tertiary objective 'To explore the impact of changes to the symptoms and threshold levels of symptoms in the LRTI case definition and severity scale' will be assessed if we detect potential areas of improvement of the LRTI case definition and severity scale, such as clearly under or overestimated incidence rates of LRTI/ severe LRTI compared to the rates in the literature or a lack of discriminative power between severe and non-severe cases. This decision will not be taken on specific pre-defined thresholds.

8. CONDUCT OF ANALYSES

8.1. Sequence of analyses

An interim analysis has been performed after data lock at the end of recruitment (expected after 18 months) or in June 2015 whichever occurs first, on the data collected for the subjects recruited in the first year of the study (approximately 1600).

Final analysis will be performed on all the data collected and cleaned in the study until 2 years of life.

The analyses will be release in a stepwise manner.

A first DBF will include all data except RVP results followed by a first statistical report. The results will be released according to a priority order defined with the team. A second DBF will add the RVP results which will be analysed in a second step and included in the statistical report.

8.2. Statistical considerations for interim analyses

A statistical analysis for the interim analysis has been performed on all the data collected and cleaned for the subjects recruited in the first year of the study, at the end of recruitment (expected after 18 months) or in June 2015 whichever occurred first.

The interim analysis has been purely descriptive, no adjustment of the type I error was foreseen.

Due to issue regarding the swab sample analysis, an additional analysis has been done in July 2017 to study the incidence.

9. CHANGES FROM PLANNED ANALYSES

- Due to the number of subjects with examination visit but without surveillance visit:
 - RSV LRTI endpoints computed using data from examination visit were added to the endpoint RSV-associated RTI with a suspicion of involvement of the lower respiratory tract definition computed using data from surveillance visit
 - The delay between LRTI identification and swab sample is not considered in the case definition
 - The subgroup analysis by collection time of swabs (72 hours/48 hours from the start date of the case (date of the call), 72 hours/48 hours from the reported onset of symptoms) has been removed
- In protocol it is suggested to analyse by country and then pool by hemisphere and region. Pooling across such diverse settings is not developing strong messages about RSV incidence and therefore we limit our subgroup analysis to by country. Where the protocol described overall incidence we have preferred to only do pooled incidence across countries by year of life. This aids meaningful interpretation and minimises tables.
- In the analysis of the key healthcare utilization and health outcomes: the hospitalization status, intensive care unit attendance, clinical diagnosis of bronchiolitis or pneumonia, death has been replaced by: outpatient visit, emergency Room visit, inpatient Admission (non intensive care), innpatient Admission (intensive care), no consultation other than site clinic and other.
- In the analysis of the performance of case definition, the key health outcome does not include intensive care unit attendance, clinical diagnosis of bronchiolitis or pneumonia and death. Instead, hospitalization status according to WHO, GSK, Nokes, and exploratory case definition will be used for the analysis.
- The incidence rates of RSV-associated LRTI/severe LRTI as classified by the GSK and Nokes case definition are not computed.
- Incidence rate of all cause RTI provided instead of per protocol non-RSV associated RTIs as RSV RTIs are subset of all cause RTI. Hence analysis of all cause RTIs is more relevant and conventional in epidemiological studies.
- Descriptive statistics of the different types of healthcare utilization will not be provided among non-RSV-associated RTI with a suspicion of involvement of the lower respiratory tract, overall and by subgroups.
- The risk factor analysis will be done using a Cox regression model and not a Poisson regression model to be consistent with the analysis performed in clinical trials.
- The sensitivity analysis will not be performed on the total enrolled cohort.
- The analysis of the impact of changes to the symptoms and threshold levels of symptoms in the LRTI case definition and severity scale will not be done by age category

200150 (EPI-RSV-005 BOD)

Statistical Analysis Plan Amendment 1 Final

- The date of study conclusion for subjects lost to follow-up will be the date of conclusion given in the CRF and will not be derived according to number of missed visits.
- Only first episode within a given age interval is considered for the computation of incidence. The incidence of event is computed using 3 different calculation methods: incidence rate, proportion affected, and incidence proportion. See section 11.1.1 for detail of calculation
- Sub-group of analysis for birth period outside or within transmission season will not be performed. Instead, the analysis will be based on the first 6 month of subject's life, and will be done considering 2 categories: <= 3 months and > 3 months. The incidence rate of RSV associate LRTI, severe LRTI, and hospitalization will be computed by country.
- Incidence and performance of case definition analysis (measures of agreement) will be performed using exploratory case definitions in anticipation of update to WHO case definitions.
- Analyses of cord blood collection using and not using recommended procedures will not be done. Instead, descriptive statistics for cord blood collection variables and cord blood levels of RSV A and B neutralizing antibodies according to cord blood collection variables will be provided. Additional analyses will be performed to evaluate disease surveillance and protocol procedures and include summary of number and percent of surveillance contacts followed by an exam visit, the duration between surveillance contact and exam visit, and duration between nasal swap and onset of symptoms.

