9.7.1. Co-primary objectives

• To determine the total health burden of RSV-associated RTI with a suspicion of involvement of the lower respiratory tract.

Incidence rates will be calculated as the number of RSV-associated RTI with a suspicion of involvement of the lower respiratory tract over the number of children-years observations, overall and by subgroups.

Descriptive statistics of the different types of healthcare utilization from all healthcare settings will be provided (proportions, duration, etc.) among RSV-associated RTI with a suspicion of involvement of the lower respiratory tract, overall and by subgroups.

• To assess the performance of the LRTI case definition and severity scale for RSV-associated cases.

Incidences rates will be calculated as the number of RSV-associated LRTI/severe LRTI as classified by the LRTI case definition and severity scale and also as classified by the comparator case definitions (WHO and Nokes, et al [Modjarrad, 2016; Nokes, 2004]), over the number of children-years observations, overall and by subgroups.

Descriptive statistics of the different types of healthcare utilization will be provided (proportions, duration, etc.) among RSV-associated LRTI/severe LRTI as classified by the LRTI case definition and severity scale and also as classified by the comparator case definitions (WHO and Nokes, *et al* [Modjarrad, 2016; Nokes, 2004]), overall and by subgroups.

Statistical analysis of agreement will be performed to compare the different case definitions of RSV-associated LRTI/severe LRTI and key healthcare utilization and health outcomes (the hospitalization status, (P) intensive care unit [ICU] attendance, clinical diagnosis of bronchiolitis or pneumonia, death) overall and by age categories.

Table 15 Comparison of two classifications for severe/Non-severe LRTI

RSV-associated cases		Classification of reference (severe/Non-severe)		
		Hospitalized	Not hospitalized	
Alternative classification (severe / Non-severe)	Severe LRTI (LRTI case definition and severity scale)	True positive (TP)	False positive (FP)	
	Non-severe LRTI (LRTI case definition and severity scale)	False negative (FN)	True Negative (TN)	

2x2 contingency tables such as Table 15 will be provided and the following measures of agreement (with 95% CI) will be calculated:

- Sensitivity: TP/ (TP+FN)
- Specificity: TN/ (TN+FP)
- Positive predictive value (PPV): TP/ (TP+FP)
- Negative predictive value (NPV): TN/ (TN+FN)

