4. ENDPOINTS

4.1. Co-primary endpoints

- Occurrence of RSV as confirmed by RT-qPCR.
- Occurrence of different types of healthcare utilization*.

* Healthcare utilization includes primary, secondary and tertiary care settings such as self-care with OTC drugs, GP visits, ER visits, hospital visits, etc.

- Occurrence of LRTI/severe LRTI as classified by the LRTI case definition and severity scale.
- Occurrence of LRTI/severe LRTI as classified by the existing comparator LRTI case definition by WHO and by Nokes et al.

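### Co-primary objective 2 is only partly answered: no incidence under the sponsor's or Kenyan definition, no age split of agreement, and a hospitalization comparison that fixes specificity and PPV at 100%

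*SAP*

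**What the plan says.** Protocol 9.7.1, under the objective on performance of the LRTI case definition and severity scale: "Incidences rates will be calculated as the number of RSV-associated LRTI/severe LRTI as classified by the LRTI case definition and severity scale", and likewise for the WHO and Kenyan comparators, overall and by subgroups. The same section plans agreement between definitions, and agreement with hospitalization, intensive care, a clinical diagnosis of bronchiolitis or pneumonia, and "death) overall and by age categories".

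SAP 4.1 keeps as co-primary "Occurrence of LRTI/severe LRTI as classified by the LRTI case definition and severity scale", and lists the two comparators beside it.

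SAP 9 says of the rates by the sponsor's and Kenyan definitions: "The incidence rates of RSV-associated LRTI/severe LRTI as classified by the GSK" (and Kenyan) "case definition are not computed". It also removes intensive care, clinical diagnosis and death from the agreement analysis, and adds exploratory definitions to both the incidence and the agreement analyses.

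SAP 7 says the sponsor's scale may be revisited for reasons "such as clearly under or overestimated incidence rates of LRTI/ severe LRTI compared to the rates in the literature", or for poor discrimination between severe and non-severe cases.

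**The concern.** Objective 2 asks how the sponsor's own scale performs, yet that scale is left without a disease rate. A later user, for example someone planning a vaccine trial with this endpoint, could not read off the rate the definition yields or set it beside the WHO rate. One of the two prompts that SAP 7 names for revising the scale could not be assessed for that scale.

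The rest of the performance assessment is also thinner than the protocol planned. Agreement is pooled over 0-23 months. Hospitalization is the only outside reference left, and the layout chosen for it cannot show over-calling by a definition. A reader of the report could take a printed specificity of 100% as a finding.

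**Working it through.** **1. Which classifications get a rate.**

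| Definition | LRTI | Severe LRTI | Source |
|---|---|---|---|
| WHO | yes | yes | Templates 7-12 |
| Sponsor | no | no | SAP 9 |
| Kenyan comparator | no | no | SAP 9 |
| Exploratory (not in protocol) | yes | yes | Templates 34-35 |

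Three protocol definitions × two severities = 6; without a rate: 4.

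**2. Can the rates be rebuilt from other tables?** No. Templates 20, 22 and 24 give episode counts for the sponsor's and Kenyan definitions, but they count all episodes, recurrences included, with no age or country split. SAP 11.1.1 counts first episodes over person-time that stops at the first episode.

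**3. Would restored rates be informative?** First, the protocol's own planning figures:
- Design effect: 1 + (160 − 1) × 0.02 = 4.18, as stated.
- 6 cases in 320 child-years, exact Poisson: 6.9 to 40.8 per 1000, as stated.
- 20 per 1000 with the design effect: 20 ± 1.96 × √(0.020 × 4.18 / 320) × 1000 = 20 ± 31.7, that is 0 to 51.7, as stated.

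Protocol 9.3 expects the RSV LRTI rate to be 8 times the hospitalization rate. With 1280 child-years:
- 20 × 8 = 160 per 1000; 0.160 × 1280 ≈ 205 cases; exact 95% CI 139.0 to 183.6, or 115.2 to 204.8 with the design effect.
- Over the protocol's range of 10 to 50: from 80 (exact 65.0 to 96.7) to 400 (exact 366.1 to 436.2).

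These are planning values for RSV LRTI generally. The documents give no expected rate for each definition.

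**4. Age.** Protocol 9.7.1 asks for agreement by age category. SAP 6.8.1 mentions none, and none of the nine Templates 20-28 has one. The only age breakdown that SAP 9 declares as dropped belongs to the tertiary objective on symptoms and thresholds. PPV, NPV and kappa depend on how common the reference condition is, and Table 12 of the protocol shows hospitalization falling from 16.9-44.1 per 1000 child-years at 0-5 months to 0.4-3.7 at 12-23 months. The Kenyan definition in protocol 4.1 also gives no respiratory-rate limit beyond 11 months, whereas SAP 11.2.2.2 applies a limit of 40 at 12-24 months. The second year is therefore where the Kenyan definition as programmed differs from the one described.

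**5. Hospitalization as reference.** In Table 4, the LRTI hospitalization category is an episode that meets the definition and was hospitalized. Templates 25-28 compare this with RSV hospitalization, so every alternative case is also a reference case:
- FP = 0
- specificity = TN/(TN + 0) = 100%
- PPV = TP/(TP + 0) = 100%

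Illustration with assumed counts: 300 RSV-positive episodes, 40 hospitalized, definition sensitivity 80% (TP 32, FN 8).

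| Specificity of definition alone | FP | PPV | NPV | Kappa | Template 25-28 layout |
|---|---|---|---|---|---|
| 90% | 26 | 32/58 = 55.2% | 234/242 = 96.7% | 0.59 | spec. 100%, PPV 100%, NPV 260/268 = 97.0%, kappa 0.87 |
| 60% | 104 | 32/136 = 23.5% | 156/164 = 95.1% | 0.20 | same |
| 20% | 208 | 32/240 = 13.3% | 52/60 = 86.7% | 0.00 | same |

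Only sensitivity is unaffected. The layout cannot tell a selective definition from one that labels nearly everything a case.

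**6. Kenyan severe rule.** Table 4 requires one of two features (low saturation with a clinical diagnosis, or chest indrawing). SAP 11.2.1.4.6 requires two of the same two, while joining them with and/or. Protocol 4.1 accepts either. A severe rate run on the derivation as written would count only children with both.

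**The case against.** Much of the assessment survives. SAP 6.8.1 keeps sensitivity, specificity, PPV, NPV, overall agreement and kappa for WHO against sponsor, WHO against Kenyan and sponsor against Kenyan, for LRTI and severe LRTI (Templates 20-23). Template 24 tabulates every definition by hospitalization status, and its percentage hospitalized is in effect the PPV that Templates 25-28 fail to give. A reader might infer that objective 2 goes unanswered; these tables show otherwise.

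A reader might also infer that the independent references have gone. Hospitalization stays. SAP 11.2.1.8 defines it without any LRTI criterion, and it is the reference in the protocol's own Table 15.

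The SAP 4.1 endpoints are worded as occurrence, not as rates, and occurrence is still counted. The clear departure is from protocol 9.7.1, and it is declared. Protocol 9.10 allows changes, with justification in the final report. SAP 7 gives incidence only as an example and sets no thresholds. The age omission is inferred from silence in the text and mock tables, and the final table list sits in a separate document. All three definitions share one respiratory-rate rule in SAP 11.2.2.2, so age-specific limits alone cannot create disagreement between them.

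These points narrow the finding. They supply no reason for omitting the rates, and saving tables is not a convincing one when exploratory rates are added. They also leave the Template 25-28 layout untouched.

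**Conclusion.** The point stands in limited form: objective 2 is partly answered. Four of six protocol classifications have no rate and no stated reason. None of Templates 20-28 is split by age, and this is undeclared. Three of four reference outcomes are removed. In Templates 25-28, specificity and PPV are fixed at 100%, which follows from the definitions and needs no assumption. The kappa values above rest on assumed counts and show direction only. That agreement varies with age is plausible from Table 12 but not established, because the documents do not give the proportion of RSV episodes hospitalized by age.

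The timing might suggest that the rates were dropped because of what they showed: SAP 8.2 reports an incidence analysis in July 2017 and this SAP is dated May 2018. The documents do not support that. The first SAP version cannot be seen, the July 2017 analysis is attributed to a swab problem, protocol Amendment 3 of December 2017 kept the rates, and the change is declared. What is missing is a justification.

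**What to change.** 1. Run Templates 7 and 9 for sponsor and Kenyan LRTI and severe LRTI, and delete the SAP 9 bullet that omits these rates. First reconcile the Kenyan severe rule between Table 4 and 11.2.1.4.6.
2. Run the between-definition agreement tables (Templates 20-23) for 0-5, 6-11 and 12-23 months as well as overall.
3. In Templates 25-28, cross-classify each definition alone against hospitalization among all RSV-positive episodes.
4. Optionally, add intensive care and clinical diagnosis as overall descriptive references only. Protocol Table 13 expects 13 to 64 hospitalizations in 1280 child-years, and intensive-care cases are a subset, so counts will be small. Provider diagnosis is optional data (protocol 6.5.14), may be missing selectively, and is part of the Kenyan definition.

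Any omission that is kept should be declared and justified in SAP 9.

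The cost is additional tables from derivations that mostly exist already (SAP 11.2.1.4.3 to 11.2.1.4.6). Templates 7 and 9 each run over five age intervals, overall and in eight countries, for four classifications, so the volume is not trivial. Age-specific agreement estimates will be imprecise and should be read as descriptive.
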